# 11. PRE-DATABASE LOCK BLINDED DATA REVIEWS

As stated previously and in the ARC003 Treatment Masking Plan and ARC003 to ARC004 Rollover Procedures document, major data queries that have or may have bearing on the efficacy and/or safety aspects of the study will be resolved prior to unblinding individual subjects. These include:

- Desensitization status from the DBPCFC (Screening and Exit)
- Major protocol deviations that might affect assignment of subjects into analysis populations,
- Fulfillment of inclusion/exclusion criteria,
- Accidental peanut exposures that resulted in SAEs or AEs
- Severity and relationship to investigational product of SAEs and AEs

The purpose of the pre-database lock blinded data review is for:

- Identification of major and minor protocol deviations (Section 5).
- Assignment of subjects to their appropriate analysis populations (Section 4).
- Classification of the treatment related and recurrent/chronic GI discontinuations (Section 8.1).
- Classification of their desensitization status (Responder or Non-responder; Section 7.4) and non-responder subcategories (Section 7.4.4).
- Classification of accidental food allergen exposures (Section 10.4) as peanutrelated or non-peanut related.

Only ARC003 project team members who are blinded to study treatment assignments (i.e., Medical Monitor, Statistician, Data Manager, Sponsor clinical project staff) will be involved in the data reviews. No member of the ARC003 project team (including data management and statistician) will have the ability to link subject identification data from ARC003 and ARC004.

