6.12 Study Blinding Procedures

This is a double-blind study. The study as a whole will not be unblinded until after the last subject exits ARC003 and the database is locked.

After undergoing the Exit DBPCFC, most subjects will, however, become de facto unblinded to their on-study treatment assignment on the basis of their experience with the food challenge; ie, subjects who fail 1 part of the Exit DBPCFC early on may reasonably deduce that they had been in the placebo arm of the study, and those who tolerate both parts of the Exit DBPCFC (or fail

1 part only at the highest dose levels tested) may reasonably deduce that they had been in the AR101 arm. Hence, the study is double-blinded on an individual subject basis only up to completion of the Exit DBPCFC. It is for this reason that assessment of reactions to DBPCFC will be made by a Blinded Evaluating Physician (Blinded Assessor).

Although the unblinding of subjects after completion of the Exit DBPCFC cannot influence the manner in which they are assessed or treated by the investigational site personnel (as their participation in ARC003 will have concluded at that time), knowledge of subjects' treatment assignments could potentially influence the investigational site personnel's conduct toward other subjects who have not yet reached the conclusion of the study. The risk of bias being introduced into the determination of DLSs during DBPCFCs due to knowledge of the treatment assignments of other subjects will be substantially reduced by having the assessment of the DBPCFC results made by a Blinded Evaluating Physician (Blinded Assessor) who is not otherwise directly involved with the treatment of the subjects he or she is evaluating. Additionally, the duration of the study and the anticipated rate of recruitment are such that that enrollment should not be influenced by the Exit DBPCFC, as enrollment should be completed before the first subjects exits the study.

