9.2.3 Supportive Analyses of Primary and Secondary Endpoints

All analyses described in Sections 9.2.1 and 9.2.2 will be repeated in the Completers and Per Protocol (PP) populations. Sensitivity analyses, using different methods to handle missing data, will be described in the SAP. In addition, a tipping point analysis to determine at what point may a variation in missing data handling overturn the primary efficacy analysis will be conducted. Details will be described in the SAP.

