# 4.4. PER PROTOCOL (PP) POPULATION

The Per Protocol (PP) population will be a subset of the Completer population, limited to subjects who have no major protocol deviations that may influence the desensitization response. Additional criteria to exclude subjects from the PP population may be added. Any changes will be documented in a SAP amendment or other supporting document. Exclusions will be determined by blinded review before database lock and overall study unblinding. Subjects will be analyzed according to randomized treatment. The PP

population differs from the Completer population only in that it excludes subjects who may have undergone the Exit DBPCFC despite having major protocol deviations.

Analyses of the primary and all secondary efficacy endpoints will be performed on the PP population if the PP population differs from Completer population by >5% in either treatment arm. Sensitivity analyses of selected endpoints may, however, be performed if the PP population differs from the Completer population by  $\leq$ 5% in both treatment arms.

The decision to conduct the optional analyses in the PP population will be made before database lock and overall study unblinding.

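### PP membership is settled by a team that may see the Exit DBPCFC outcome, and the SAP makes the PP analyses conditional where the protocol does not

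*SAP*

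**What the plan says.** **Who reviews, and what.** SAP Section 11 limits the pre-lock reviews to "Only ARC003 project team members who are blinded to study treatment assignments". Their purposes include grading deviations as major or minor, "Assignment of subjects to their appropriate analysis populations (Section 4") and "Classification of their desensitization status (Responder or Non-responder; Section 7.4) and non-responder subcategories (Section 7.4.4"). No order is given, and nothing says that the reviewers of deviations do not see the Exit DBPCFC result.

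**What decides PP membership.** SAP 4.4 takes the Completer set, "limited to subjects who have no major protocol deviations that may influence the desensitization response". It allows exclusion criteria to be added with documentation, and requires exclusions to be settled by blinded review before lock.

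**When PP is analysed.** SAP 4.4 requires the PP analyses "if the PP population differs from Completer population by >5% in either treatment arm". If the difference is 5% or less in both arms, they may be run on selected endpoints. It adds: "The decision to conduct the optional analyses in the PP population will be made before database lock and overall study unblinding". SAP 9.2 and 9.4 repeat the condition and refer to a section 4.7, but Section 4 ends at 4.4. Protocol 9.2.3 has no condition: "All analyses described in Sections 9.2.1 and 9.2.2 will be repeated in the Completers and Per Protocol (PP) populations".

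**What the outcome reveals.** Protocol 6.12 says that after the Exit challenge "most subjects will, however, become de facto unblinded to their on-study treatment assignment". SAP 2.5 says the same of the investigator, as a possibility.

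**Role of PP.** ITT is the primary set for efficacy (SAP 4.2) and carries the primary and key secondary hierarchical tests (SAP 9.1, 9.3).

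**The concern.** A PP analysis is useful as a check only if membership is decided without regard to the result. Here the same people may hold the deviation record and the challenge outcome together, and must judge whether a deviation could have affected desensitization. Blinding to the treatment code does not blind them to outcome, and in this trial outcome is a clue to arm. Protocol 6.12 states the aim of keeping population allocation free from knowledge of treatment, and showing allocators the result works against that aim.

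The second problem is separate. The PP condition is defined by arm, while the choice about the optional analyses is due before anyone on the team may know the arm. The protocol promises the analyses without any condition. At stake is whether a planned robustness check is run at all, and on a set whose selection can be defended.

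**Working it through.** The plan gives no figure on this point, so there is none to reproduce. Completion rates below are assumptions, since the documents give none for this trial.

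**Inputs.** 495 children, 3:1, about 371 and 124 (Protocol 9.4); SAP 2.4 also gives 499, about 374 and 125. Planned 600 mg response 50% and 20% (Protocol 9.4). In ARC001, 23 of 29 AR101 subjects reached the Exit challenge and 18 of those 23 tolerated 600 mg; all 26 placebo subjects completed and none tolerated 600 mg (Protocol 1.2.2.1).

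**1. How far outcome reveals arm** (Bayes' rule, prior 0.75 for AR101).
- Responder, planned rates: 0.75×0.50 / (0.75×0.50 + 0.25×0.20) = 0.375/0.425 = 0.88.
- Non-responder, planned rates: 0.375 / (0.375 + 0.25×0.80) = 0.375/0.575 = 0.65.
- ARC001 completer rates: every responder is on AR101. For a non-responder, P(placebo) = 0.25 / (0.25 + 0.75×(23/29)×(5/23)) = 0.25/0.379 = 0.66.

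**2. What outcome-related exclusion could do**, taking all 495 as completers at 50% and 20% (difference 30.0 points).
- Remove 24 non-responders regardless of arm. Non-responders number 185.5 and 99.2, so about 15.6 and 8.4 leave: 185.5/355.4 − 24.8/115.6 = 52.2% − 21.4% = 30.8 points.
- Remove about 5% of each arm in the direction favouring AR101 (18 AR101 non-responders, 6 placebo responders): 185.5/353 − 18.8/118 = 52.5% − 15.9% = 36.6 points.
- One-arm bound: 374 AR101 children, 80% completing (299), 187 responders, gives 187/299 = 62.5%. Dropping 18 (6%) gives 187/281 = 66.5% if all are non-responders and 169/281 = 60.1% if all are responders, that is +4.0 or −2.4 points.

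**3. When the trigger can be read blind.** With completers n1 and n2, neither arm can exceed 5% if total exclusions are at most floor(0.05×n2), n2 being the smaller arm. At least one arm must exceed 5% once the total is above floor(0.05×n1) + floor(0.05×n2). Between these limits the arm split is needed.

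| Completers (AR101 : placebo) | Undetermined exclusions | Pooled % |
|---|---|---|
| 371 : 124 (all complete) | 7–24 | 1.4–4.8 |
| 293 : 124 (79%, 100%) | 7–20 | 1.7–4.8 |
| 223 : 112 (60%, 90%) | 6–16 | 1.8–4.8 |

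Example with 299 and 119 completers (80% of 374, about 95% of 125) and 16 exclusions (3.8%). One placebo exclusion gives AR101 15/299 = 5.02%, so the rule is met. Two give 14/299 = 4.7% and 2/119 = 1.7%, so it is not. Six give 6/119 = 5.04%, so it is met again.

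**The case against.** Several points on the other side stand.

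- A reader might infer that the trigger lets exclusions follow the outcome. It does not: it decides whether PP is analysed, never who is in it.
- A reader might also infer that the rule is unworkable without breaking the blind. The timing sentence covers only the optional branch. The mandatory branch could be applied after unblinding to a set already frozen, and the optional choice could be recorded in advance as a conditional statement. Outside the ranges above, pooled counts suffice. The SAP does not, however, say that it will work this way.
- Safeguards exist. Exclusions are fixed blind to treatment and before lock, added criteria must be documented, deviations are recorded in listed categories (SAP 5), and responder status follows set rules (SAP 7.4).
- SAP 11 speaks of reviews in the plural, and the Treatment Masking Plan, which is not among the documents, might set an order. The finding is that the SAP and protocol state none.
- Masking everything about the Exit challenge would stop reviewers grading departures in how it was conducted, which are among the deviations most able to affect response. The fix has to allow for this.
- Sponsor clinical project staff have data access throughout (SAP 2.5), and queries on desensitization status are resolved before each subject is unblinded (SAP 11). Masked listings therefore reduce exposure to outcome without guaranteeing its absence.

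None of this answers the missing sequence in Section 11 or the conflict between SAP 4.4 and Protocol 9.2.3.

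**Conclusion.** Two separate, modest defects hold, both confined to a supportive analysis.

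First, the SAP leaves room for PP exclusions to be influenced by outcome. This is a possibility created by the missing sequence, not evidence that it will happen. Exclusion by outcome alone barely moves the treatment difference (30.0 to 30.8 points in the illustration). A large shift (to 36.6) needs exclusions aligned with arm, which outcome only partly reveals at the planned rates but reveals more fully at ARC001 rates. A reader might take the 6.4 points between 66.5% and 60.1% as the expected bias. It is the distance between two opposite extremes in one arm and rests on assumed completion.

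Second, the per-arm condition cannot be read blind when pooled exclusions are roughly 1.4% to 4.8%, and it contradicts the protocol's unconditional commitment. SAP 12, headed as covering changes from the protocol's analysis, does not record the difference.

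The documents do not support extending either point to the primary result or to the Type I error of the key secondary hierarchy.

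**What to change.** **SAP 11.** State the order: grade deviations and sign off PP membership first, then classify responders. The first step should use listings that omit responder status, MTD, symptom severity, exit ps-IgE and IgG4, and exit SPT. The listings should keep whether the Exit peanut challenge was completed, which the Completer definition needs, and any deviation in how the challenge was conducted, described without its result.

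**SAP 4.4, 9.2 and 9.4.** Delete the 5% condition and the optional branch, run the PP analyses unconditionally as Protocol 9.2.3 states, and correct the reference to section 4.7.

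**Cost.** SAP wording, one listing specification and one set of tables. Describing conduct deviations without the result takes some care in preparing the listing. No data collection or trial conduct changes.

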#### 12. CHANGE FROM ANALYSIS PLANNED IN PROTOCOL

Any deviations from the plans detailed in this SAP will be described and justified in the final clinical study report. A separate document to this SAP will provide a table of contents and mockups for the expected layout and titles of the tables, listings, and figures. Any changes to format, layout, titles, numbering, or any other minor deviation will not necessitate a revision to the SAP nor will it be considered a deviation from planned analyses. Only true differences in the analysis methods or data handling will necessitate such documentation.

## 14. **PROGRAMMING CONSIDERATIONS**

All tables, data listings, figures (TLFs) will be generated using SAS® for Windows, Release 9.4 or higher (SAS® Institute Inc., Cary, NC, USA). Computer-generated table, listing and figure output will adhere to the following specifications.

## 14.1. GENERAL CONSIDERATIONS

Report summaries will be generated using validated Base SAS® software, version 9.4 or higher, on a PC or server-based platform. Additional validated software may be used to generate analyses, as needed.

Data will be analyzed by Agility Clinical biostatistics personnel. Statistical analyses will be reported with tables, figures, and listings, presented in rich text format, and using recommended ICH numbering. Output specifications for all tables, figures, and listings will be in conformance with guidelines specified by the ICH in Appendix 7 of the *Electronic Common Technical Document Specification* (Apr 2003).

# 14.2. **REPORTING CONVENTIONS**

Tables and figures will be summarized by treatment group. Tables summarizing demographics and other baseline characteristics will also include a column for all subjects combined. In general, all data collected and any derived data will be presented in subject data listings, for all randomized subjects. Listings will be ordered by age group, treatment group, subject number, and assessment or event date. The treatment group presented in listings will be based on the planned assignment, unless otherwise noted.

In general, continuous variables will be summarized to indicate the population sample size (N), number of subjects with available data (n), mean, SD, median, minimum, and maximum values. Categorical variables will be summarized by the population size (N), number of subjects with available data (n), number of subjects in each category, and the percentage of subjects in each category. Unless otherwise noted, the denominator to determine the percentage of subjects in each category will be based on the number of subjects with available data. Select ordinal data may be summarized using both descriptive statistics and counts and percentages of subjects in each category, as appropriate.

Non-zero percentages will be rounded to one decimal place. Rounding conventions for presentation of summary statistics will be based on the precision of the variable of summarization, as it is collected in its rawest form (ie, on the electronic case report form [eCRF] or as provided within an external file) and are outlined as follows:

• The mean and median will be rounded to one more decimal place than the precision of the variable of summarization;

- Measures of variability (eg, SD, SE) will be rounded to two more decimal places than the precision of the variable of summarization; and
- Minimum and maximum values will be presented using the same precision as the variable of summarization.

Other statistics (eg, CIs) will be presented using the same general rules outlined above, or assessed for the most appropriate presentation based on the underlying data.

Statistical significance testing will be two-sided and performed using  $\alpha$ =0.05. P-values will be reported for all statistical tests, rounded to four decimal places. P-values less than 0.0001 will be displayed as "<0.0001"; p-values greater than 0.9999 will be displayed as ">0.9999". Tests of interaction terms, if applicable, will be two-sided and performed using  $\alpha$ =0.10.

Unless otherwise noted, values reported as greater than or less than some quantifiable limit (eg, "< 1.0") will be summarized with the sign suppressed in summary tables and figures, using the numeric value reported. Data will display on subject listings to include the sign.

# 15. QUALITY CONTROL

All SAS programs that create outputs or supporting analysis datasets will be validated by a second statistical programmer or biostatistician. At a minimum, validation of programs will consist of a review of the program log, review of output or dataset format and structure, and independent confirmatory programming to verify output results or dataset content. Additionally, all outputs will undergo a review by a senior level team member before finalization.

The content of the source data will be reviewed on an ongoing basis by project statistical programmers and statisticians. Data will be checked for missing values, invalid records, and extreme outliers through defensive programming applications, analysis-based edit checks, and other programmatic testing procedures. All findings will be forwarded to the project data manager for appropriate action and resolution.

#### **16. STUDY SCHEDULE**

Refer to the protocol for the full study schedule of events (Appendix 1)

#### 17. INDEX OF TABLES, LISTINGS AND FIGURES

An index of the planned statistical outputs will be provided in the shell TLF document.
